3.5.4 Pharmacokinetic Parameters

The following PK parameters will be calculated from the individual concentration, including Day 0 PK concentration data through Day 28 predose concentration data, Day 140, Day 336, and Day 700.

Parameters	Description
C_{max}	Maximum drug concentration; observed directly from the data. If not unique, then the first maximum concentration is used
T_{max}	Time to $C_{max, D1}$
C_{last}	The last measurable concentration
T_{last}	Time of C_{last}
AUC_{0-28d}	Area under the concentration-time curve (AUC) from time 0 to the time of the last measurable concentration (C_{last}) to Day 28 predose
RClast	Accumulation ratio based on C_{last} ; calculated as C_{last} after multiple dose divided by C_{last} after the first dose (Days 140, 336, 700)
RCmax	Accumulation ratio based on C_{max} ; calculated as C_{last} after multiple dose divided by C_{max} after the first dose (Days 140, 336, 700)

Actual collection times will be used in PK parameter calculations. The Linear-Log Trapezoidal method (equivalent to the Linear Up/Log Down option in WinNonlin) will be used in the computation of all AUC values.

No PK parameters will be calculated for subjects with 2 or fewer detectable concentrations in their PK profile.

AUC may not be calculated for the subjects that only have one measurable postdose PK concentration.

If a subject has only one non-zero concentration at the 2 hours post dose time point, C_{last} will not be calculated for this subject.

The latent myostatin concentrations will be listed for each patient and summarized by separated cohorts.

The BLQ values of latent myostatin will not be imputed and set as missing.

Anti-drug antibody data will be listed and summarized in tabular format reporting positive count and percentage. Confirmed positive samples will be further tested for the presence of neutralizing activity.

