- ^d Females of childbearing potential only. Urine or serum test is acceptable; however, positive urine tests must be confirmed with serum testing. Testing may be performed more frequently as per local requirements. The urine pregnancy test used is the Alere hCG cassette (25mIU/mL) and according to the product manufacturer, has >99% sensitivity.
- ^e Weight is collected within 48 hours of each dose to calculate weight-based dosing.
- ^f Height is collected at visits where the motor function outcome measures are conducted. Ulna length may be used to estimate height for patients who are nonambulatory or needs standing support.
- ^g Changes in pubertal development must be assessed if not deemed physically mature at Screening. If menarche occurs during the study, the child will be deemed of childbearing potential and immediate pregnancy status will be checked. Further study drug can only be given if pregnancy status is negative. Contraception and pregnancy monitoring will be performed as outlined in the protocol.
- ^h Heart rate, blood pressure, and respiratory rate are collected preinfusion, every 15 minutes (\pm 5 minutes) during the infusion, at the end of the infusion, and 1 and 2 hours (\pm 15 minutes) postinfusion. Body temperature will be collected preinfusion on dosing days.
- ⁱ Clinical safety labs include serum chemistry, hematology, urinalysis, and coagulation. Labs are collected preinfusion at dosing visits.
- ^j 12-lead ECGs are collected after 5 minutes of rest, in triplicate and at least 1-2 minutes apart. ECGs are collected within 2 hours prior to the start of the infusion. Unscheduled ECGs may be performed as clinically necessary.
- ^k Blood samples for PK and PD are collected within 2 hours prior to the start of the infusion at dosing visits. An additional sample is collected via peripheral IV 2 hours (\pm 1 hour) after completion of the infusion on Day 0, Day 140 (PK only), and Day 336 (PK only).
- ^l Blood sample for anti-SRK-015 antibody testing is collected within 2 hours prior to the start of the infusion at dosing visits.
- ^m Patients in Cohort 3 will be randomized to low or high-dose SRK-015 within 24 hours prior to the first infusion on Day 0.
- ⁿ See Table 5 for motor function outcome measures conducted for each cohort. Unscheduled motor function outcome measures may be performed as needed.

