- ^o QOL collected using the PROMIS Fatigue Questionnaire and PEDI-CAT. If the PEDI-CAT and/or PROMIS are not available in the native language, they should not be completed. Unscheduled QOL questionnaires may be performed as needed.
- ^p Sites contact patients within 7 days following each infusion to collect information on adverse events and concomitant medications.

Table 4: Study Schedule of Assessments: Extension Period A (Extension A Visits 1-15)

Activity/Assessment	Extension Period A														Follow-Up/Other			
	Visit Time Point (Study Day ^a)	E1 364 ^c	E2 392	E3 420	E4 448	E5 476	E6 504	E7 532	E8 560	E9 588	E10 616	E11 644	E12 672	E13 700	E14 728	E- UNS	E15 EOS/ ET	
Informed Consent ^o	X																	
Pregnancy Test ^d	For patients who enroll into Extension Period A, assessments will merge between Treatment Period Day 364 (V15) and Extension Period A Day 364 (E1). Study drug administration and PK/PD/ADA Sampling will only be performed for patients who enroll into Extension Period A.		X				X				X						X	
Weight ^f		X	X	X	X	X	X	X	X	X	X	X	X	X	X	X	X	X
Height ^f						X				X					X	X	X	X
Physical Examination ^g		X			X		X		X		X		X		X	X	X	X
Vital Signs ^h		X	X	X	X	X	X	X	X	X	X	X	X	X	X	X	X	X
Clinical Safety Labs ⁱ		X				X			X			X		X		X	X	X
12-lead ECG ^j		X				X			X			X		X		X	X	X
PK and PD Sampling ^k		X	X			X			X			X		X	X	X	X	X
Antidrug Antibody Sampling ^l	X	X			X			X			X		X	X	X	X	X	
Study Drug Administration	X	X	X	X	X	X	X	X	X	X	X	X	X					
Motor Function Outcome Measures ^{b,f,m}					X				X					X	X	X	X	
QOL ⁿ					X				X					X	X	X	X	
Adverse Events	To be collected from the date that the ICF is signed through the last study visit																	
Concomitant Therapy	To be collected from the date that the ICF is signed through the last study visit																	

ECG = electrocardiogram; EOS = end-of-study; ET = early termination; ICF = informed consent form; IV = intravenous; PD = pharmacodynamic; PEDI-CAT: Pediatric Evaluation of Disability Inventory Computer Adaptive Test; PK = pharmacokinetic; PROMIS = Patient-reported Outcomes Measurement Information System; QOL = quality of life; UNS = unscheduled.

- ^a Study visits have a ± 7 -day window. Visit assessments may be conducted over multiple days within the visit window, as needed and in compliance with protocol requirements for the timing of each assessment.
- ^b All motor function outcome measures will be conducted within 96 hours prior to dosing.

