2.3.3 Pharmacokinetics (PK), Pharmacodynamics (PD), and Immunogenicity Endpoints

2.3.3.1 Pharmacokinetics Blood Sample Collection

Blood samples for the measurement of SRK-015 concentrations will be obtained prior to study drug infusion as indicated in the schedule of assessments in Table 3, Table 4, and Table 5. In the Treatment Period, the 2-hour (\pm 1 hour) postdose (from the stop of the infusion) sample collection on Day 0, Day 140, and Day 336 must be collected via peripheral venipuncture. In Extension Periods A and B, the 1-hour (+30-minute window) postdose (from the stop of the infusion) sample collection on Day 700 and Day 1008 must be collected via peripheral venipuncture.

Each collected sample will be split into approximately equal volume sample sets to allow for retesting, if required. Aliquots from the PK blood samples may be used for additional immunogenicity or PD testing as appropriate, and Baseline and postdose samples may be used to support PK, PD and/or ADA assay validation.

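### SAP 3.5.4 labels RCmax a Cmax-based accumulation ratio but puts Clast in its numerator, so with a trough as Clast it does not measure peak accumulation

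*Combined protocol and SAP*

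**What the plan says.** SAP 3.5.4 defines two accumulation ratios, both for Days 140, 336 and 700. RClast, described as based on Clast, is "calculated as C_{last} after multiple dose divided by C_{last} after the first dose". RCmax, described as based on Cmax, is "calculated as C_{last} after multiple dose divided by C_{max} after the first dose". Clast itself is only the final measurable value; no sample is named.

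The section takes its parameters from individual concentrations, "including Day 0 PK concentration data through Day 28 predose concentration data, Day 140, Day 336, and Day 700". The first-dose profile therefore has a stated end, the Day 28 predose sample, while the later days are listed without one. A further rule reads "If a subject has only one non-zero concentration at the 2 hours post dose time point, C_{last} will not be calculated for this subject".

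On sampling, SAP Table 3 (section 2.2.4, footnote k) says "Blood samples for PK and PD are collected within 2 hours prior to the start of the infusion at dosing visits". SAP 2.3.3.1 adds a sample 2 hours after the end of infusion: "sample collection on Day 0, Day 140, and Day 336 must be collected via peripheral venipuncture". Day 700 has one at 1 hour after the end of infusion.

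No other section redefines RCmax. Protocol 11.2.3 lists no PK parameters, SAP 3.5.2 and 3.5.3 deal with handling and display of concentrations, and the list of changes in SAP section 6 does not mention it.

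**The concern.** A ratio called Cmax-based should compare a later peak with the first peak. This one compares a later Clast with the first peak. The RClast row directly above has the same numerator, so a copy-down slip is likely, but the text does not show which was meant.

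A programmer who follows the SAP literally and takes a trough as Clast would report a trough-to-peak ratio under an accumulation label. A value below 1 would then suggest no accumulation when peaks are in fact rising. Characterizing PK is a secondary objective, so the table would be read.

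**Working it through.** The documents state no PK ratio, so there is no figure to reproduce. The check is first textual, then an illustration of size.

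**1. The two rows side by side**

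| Row | Label says | Numerator (later dose) | Denominator (first dose) |
|---|---|---|---|
| RClast | based on Clast | Clast | Clast |
| RCmax | based on Cmax | Clast | Cmax |

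Only the RCmax row disagrees with its own label.

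**2. Which sample Clast could be**

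After the first dose the scheduled PK samples are Day 0 predose, Day 0 postdose, Day 14 and Day 28 predose. First-dose Clast is thus normally the Day 28 predose trough, and first-dose Cmax is normally the Day 0 postdose value. For Days 140, 336 and 700 the candidates are the same-visit predose, the next-visit predose, or the same-day postdose sample.

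**3. Size if Clast is a trough**

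Inputs: dosing every 28 days, so Days 140, 336 and 700 are doses n = 6, 13 and 26; a 2-hour infusion; half-life t½ of 23 to 33 days (Protocol 4.4, Phase 1 single-dose data in healthy adults). Assumed: linear PK and constant dose.

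By superposition, the peak after dose n is the first-dose peak plus what remains from earlier doses, and the same-visit predose value is that remainder. Dividing both by the first peak gives

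true RCmax − RCmax as written ≈ 1.

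This needs no particular disposition model, because the remainder hardly changes in the few hours between the two samples.

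For one compartment, ignoring infusion time, let r = 2^(−28/t½), which is 0.430, 0.500 and 0.555 for t½ = 23, 28 and 33 days.

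- Peak ratio = (1 − r^n)/(1 − r)
- Same-visit predose over first peak = (r − r^n)/(1 − r), exactly 1 less

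Example, Day 140 and t½ = 23: (1 − 0.430^6)/(1 − 0.430) = 1.74, and 1.74 − 1 = 0.74. With the infusion and the actual sampling times included the second value is 0.75.

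Full one-compartment results for t½ = 23 / 28 / 33 days:

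| Day | Peak over peak | As written, same-visit predose | As written, next-visit predose |
|---|---|---|---|
| 140 | 1.74 / 1.97 / 2.18 | 0.75 / 0.97 / 1.19 | 0.75 / 0.99 / 1.22 |
| 336 | 1.75 / 2.00 / 2.25 | 0.76 / 1.00 / 1.25 | 0.76 / 1.00 / 1.25 |
| 700 | 1.76 / 2.00 / 2.25 | 0.76 / 1.00 / 1.25 | 0.76 / 1.00 / 1.25 |

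The gap is 0.97 to 1.00 throughout.

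**4. Sensitivity to the model**

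Suppose half of the initial concentration decays with a 2-day half-life and the other half with the 23 to 33 day half-life. This split is an assumption, not a figure from the documents. Peak over peak is then 1.38–1.65 and the as-written RCmax 0.38–0.64. The levels move a good deal; the gap stays at about 1.

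**5. Size if Clast is the same-day postdose sample**

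The as-written RCmax then equals the peak ratio, 1.74–2.25 with one compartment. But RClast becomes a later peak over the Day 28 trough: 3.9–4.1 with one compartment (5.6–6.3 with the distribution phase), against 1.73–2.25 for trough over trough. No single reading makes both rows like for like.

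**The case against.** The best defence is that this is a one-symbol slip that a PK analyst would correct on sight. Clast is also less open than it looks. The first-dose profile ends at a predose sample, a lone 2-hour value is refused as Clast, and SAP 3.5.2 has a separate rule for values below quantification at trough. All three point to a trough. Which trough is used barely matters: in the one-compartment illustration the choice changes RClast by at most about 0.05 on Day 140 and hardly at all later. SAP section 7 also places programming and derived-data specifications in separate documents, which may name the sample. All of this stands, and it makes the peak-over-trough outcome for RClast the less likely one. It does not cure the RCmax row: the more firmly Clast is a trough, the more clearly that formula is wrong.

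A reader might also infer that the ratios could never be calculated, because the SAP says "No PK parameters will be calculated for subjects with 2 or fewer detectable concentrations in their PK profile" and each later dosing day has only two scheduled PK samples. The text does not support that. The rule is worded per subject, and the section's opening sentence takes the first-dose data and the later days together, so a normally sampled patient has more than two concentrations.

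**Conclusion.** The RCmax definition contradicts its label and should be corrected. It is an inconsistency of definition, not a miscalculated figure. With Clast as a trough, the reported value is about 1 too low and can fall below 1 while the drug accumulates. That gap rests on linear PK and constant dose, so it does not describe Cohort 3 patients whose dose changed before Day 700. The absolute ratios also depend on the assumed model and on a healthy-adult half-life, and should be read as illustration only.

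Severity is minor. A reader might infer that dose selection or the trial's conclusions are affected; the documents give no basis for that. RCmax is a descriptive parameter under a secondary objective, no dose, safety or efficacy decision refers to it, and the PK interim at which dose levels may be adjusted is triggered after at least two doses, whereas the first of these ratios needs the sixth. SAP 3.5.3 lists individual concentrations, so the peak ratio can be recovered.

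**What to change.** 1. In SAP 3.5.4, define RCmax as Cmax after multiple dose divided by Cmax after the first dose (Days 140, 336, 700), using the postdose samples already scheduled on Days 0, 140, 336 and 700.
2. Add one sentence stating that Clast in RClast is a predose trough, compared with the Day 28 predose trough, and name the sample: same visit or next visit, applied consistently. Either serves. For Day 336 the next-visit sample falls on Day 364, and the Extension Period A schedule notes that "Study drug administration and PK/PD/ADA Sampling will only be performed for patients who enroll into Extension Period A", so that choice loses Day 336 RClast for patients who do not continue.

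The cost is one symbol and one sentence, with no new samples. If the PK tables have already been programmed, the RCmax column should be checked and, if needed, rerun from existing data.

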3.6 Safety Assessment

Safety data will be evaluated for vital signs, laboratory outcomes, ECGs, and AEs. Clinically significant outcomes will be noted. All safety analyses will be performed on the Safety Population in each cohort, by cohort, by dose (combining all cohorts), and by patients being treated with and without an approved SMA treatment, and the entire Safety Population.

3.6.1 Adverse Events (AEs)

A summary overview of TEAEs will be provided, which presents the number and percentage of patients in each cohort and dose level from the Safety Population satisfying each of the following categories:

- Any AEs,
- Any SAEs,
- Any TEAEs,
- Any AEs leading to death,
- Any AEs leading to study drug discontinuation,
- Any SAEs leading to death,
- Any SAEs leading to study drug discontinuation,
- Any TEAEs leading to death, and
- Any TEAEs leading to study drug discontinuation,

Adverse events will be coded using the Medical Dictionary for Regulatory Activities (MedDRA) version 23.0 or later. The number and percentage of patients with specific criteria will be summarized by their MedDRA preferred term within system organ class and by treatment within each cohort. These summaries will include patients with the following criteria: TEAEs, SAEs, TEAEs with severity of Grade 3 and above, drug related TEAEs, TEAEs present in 5% or more of patients, and various categories of TEAEs by Time (on or before Week 12 vs. Post Week 12). For patient count summaries, multiple AE events with the same MedDRA coded terms (preferred term and system organ class) from the same patient will only be counted once.

The number and percentage of patients with TEAEs will be summarized by reported maximum severity within each MedDRA preferred term within system organ class and by dose-level within each cohort.

All SAEs will be listed with an indication of whether the SAE was treatment emergent or started prior to treatment. All TEAEs that are reported as leading to study drug discontinuation will be listed. TEAEs leading to death, if applicable, will be listed.

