6. INVESTIGATIONAL PLAN

6.1. Overall Study Design

Study SRK-015-002 is an active treatment study of SRK-015 in patients age 2 through 21 years old with later-onset SMA. Patients may receive SRK-015 as monotherapy or in addition to an SMN upregulator therapy approved for SMA.

The study will be conducted at approximately 20 study sites across the US and Europe and will enroll approximately 55 patients with SMA across 3 separate parallel subpopulations subsequently described as cohorts:

- Cohort 1, N=20: Ambulatory Type 3 patients, age 5 through 21 years old, at least 10 of whom are not receiving an approved SMA treatment, as well as patients already receiving an approved SMA treatment that had been started after the patient turned 5 years old.
- Cohort 2, N=15: Type 2 or nonambulatory Type 3 patients, age 5 through 21 years old, already receiving an approved SMA treatment that had been started after the patient turned 5 years old.
- Cohort 3, N=20: Type 2 patients, age ≥ 2 years old, already receiving an approved SMA treatment that had been started before the patient turned 5 years old.

Patient participation in the study will consist of 3 parts: Screening, Treatment, and Follow-up.

1. During the Screening Period, all patient screening and eligibility determinations will be conducted after informed consent (and, as required by local authorities, patient informed assent) has been provided and within 28 days prior to first dose. Screening motor function outcome measures will be conducted at least 7 days prior to the first dose. All subsequent motor function outcome measures will be conducted within 96 hours prior to dosing.
2. During the 52-week Treatment Period, patients enrolled in Cohorts 1 and 2 will receive high-dose (20 mg/kg) SRK-015 and patients enrolled in Cohort 3 will be randomized (1:1) in a blinded manner to receive either low-dose (2 mg/kg) or high-dose (20 mg/kg) SRK-015 (Figure 1). All treatments will be administered by IV infusion over approximately 2 hours once every 4 weeks. The first dose will be administered on Day 0 and the final dose on Day 336, for a total of 13 doses. There will be a ± 7 -day window around each dosing visit, with a minimum of 21 days and a maximum of 35 days between doses.

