7.4. Patient Rescreening, Replacement, and Over-enrollment

A patient who is determined to be eligible based on screening assessments and experiences an acute or comorbid condition that causes a delay in their Baseline visit and first infusion (Day 0) may remain eligible up to an additional 14 days after the end of the Screening Period without having to rescreen. The patient may proceed with entering the Treatment Period after the resolution of the event and if deemed safe to do so by the Investigator. Screening patients who experience an acute clinical event that results in a delay of more than 14 days outside of the Screening Period must rescreen to determine eligibility.

Patients who withdraw from the study for reasons that are not related to safety before receiving 4 doses of SRK-015 and undergoing 2 postdose HFMSE or RHS assessments may be replaced at the discretion of the Sponsor.

Patients who are in the Screening Period at the time a cohort has enrolled its required number of patients may continue to be enrolled after they are determined to be eligible.

To preserve the robustness of the analyses, the Sponsor may enroll additional patients into a cohort as a result of patients in that cohort who significantly change their background approved SMA treatment while on study (e.g., a patient discontinues nusinersen or begins a new approved treatment as part of standard of care for their SMA).

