10.3. Adverse Event Monitoring

Each patient will be monitored for the occurrence of AEs, including SAEs, from the signing of the ICF through the final follow-up visit.

- Patients will be questioned and/or examined by the Investigator or a qualified designee for evidence of AEs. The questioning of patients with regard to the possible occurrence of AEs will be generalized such as, “How have you been feeling since your last visit?” The presence or absence of specific AEs should not be elicited from patients.
- Patients having AEs will be monitored until resolution or stabilization (in the case of persistent impairment), or until the event becomes chronic in nature, or the patient dies.
- AEs, actions taken as a result of AEs, and follow-up results must be recorded in the eCRF as well as in the patient's source documentation. Follow-up laboratory results should be filed with the patient's source documentation.

For any SAEs or AEs that require the patient to be discontinued from dosing, relevant clinical assessments and laboratory tests will be repeated as clinically appropriate, until final resolution or stabilization of the event(s). Patients will continue to be followed through 12 weeks after the final dose.

All safety laboratory analyses will be performed at a central laboratory. The clinical laboratory values will be reported to the Investigator who will review them for clinical significance and consideration of abnormal values as potential AEs.

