10.7. Reporting Serious Adverse Events

10.7.1. Serious Adverse Event Reporting

10.7.1.1. Initial Reports

All SAEs occurring from the time of informed consent through the final study visit must be reported to PPD within 24 hours of the awareness of the occurrence (this refers to any AE that meets any of the aforementioned serious criteria). (Note: The change in reporting from Medpace to PPD became effective on 20 May 2021). All SAEs that the Investigator considers related to study drug occurring after the study must be reported to the Sponsor.

To report the SAE, the SAE form will be completed electronically in the electronic data capture (EDC) system for the study. When the form is completed, PPD Safety personnel will be notified electronically and will retrieve the form. Any supporting documentation (e.g., discharge summary, diagnostic results) must be redacted by the site and emailed or faxed to PPD (contact information below).

If the EDC system cannot be accessed for technical reasons and the event meets serious criteria, complete the back-up paper SAE form and send via email or fax to PPD (contact information below) or call the PPD SAE reporting line (phone number listed below). When the EDC system becomes available, the SAE information must be entered within 24 hours of the system becoming available.

Safety Contact Information: PPD

PPD SAE reporting line – USA/Canada:

[contact]

[contact]

PPD SAE Hotline – Europe:

[contact]

[contact]

Email: [contact]

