SAP	Statistical Analysis Plan
SDTM	Study Data Tabulation Model
SMA	Spinal Muscular Atrophy
SMN	Survival Motor Neuron
SST	Safety Surveillance Team
TEAE	Treatment-emergent Adverse Event
TE-SAE	Treatment-emergent Serious Adverse Event
WHO	World Health Organization

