2.3.2.2 Treatment-Emergent Adverse Events

Treatment-emergent adverse events (TEAEs) are defined as those AEs satisfying one of the following:

- Occur after the first administration of study drug; or
- Occur prior to the administration of study drug and worsen in severity/grade or relationship to investigational medication after the administration of study drug.

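### The by-dose SAE tables in SAP 3.6.1 are not limited to treatment-emergent events; a treatment-emergent SAE count should be added beside the all-SAE count

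*Combined protocol and SAP*

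**What the plan says.** SAP 3.6.1 plans two kinds of SAE table on the Safety Population.

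- **Overview, by cohort and dose level.** It is introduced as an overview of TEAEs, but it has separate rows for any AEs, any SAEs and any TEAEs. Each of the three also has a row for events leading to death and one for events leading to study drug discontinuation.
- **Tables by system organ class and preferred term, by treatment within cohort.** "These summaries will include patients with the following criteria: TEAEs, SAEs, TEAEs with severity of Grade 3 and above, drug related TEAEs". The list continues with TEAEs in 5% or more of patients and TEAEs by time.

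The same section adds a listing: "All SAEs will be listed with an indication of whether the SAE was treatment emergent or started prior to treatment".

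On collection, Protocol 10.3 states: "Each patient will be monitored for the occurrence of AEs, including SAEs, from the signing of the ICF through the final follow-up visit". Protocol 10.7.1.1 states: "All SAEs occurring from the time of informed consent through the final study visit must be reported to PPD within 24 hours".

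The SAP abbreviation list expands TE-SAE as "Treatment-emergent Serious Adverse Event", but SAP 3.6.1 does not use the term.

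**The concern.** Safety and tolerability is a primary objective, and the trial has no placebo arm. Readers will take an SAE percentage in a dose column as a description of what happened on that dose. As specified, the column can also contain events that began before any drug was given.

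Cohort 3 shows this most clearly. Patients there are randomized within 24 hours before the first infusion (footnote m to the Treatment Period schedule). Almost any SAE during Screening therefore precedes arm assignment and cannot be a dose effect. It would nevertheless be counted in one of two columns of about 10 patients, and the heading of the overview invites the reader to regard it as treatment-emergent.

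**Working it through.** The plan states no figure on this point, so there is none to reproduce. The check is mainly one of wording, with some arithmetic for scale.

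**1. Does SAE, as the SAP uses it, include pre-dose events?** Yes. Collection starts at consent (Protocol 10.3 and 10.7.1.1), and the listing must mark which SAEs started before treatment. That mark would have no purpose if the term already excluded them.

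**2. Does the overview heading limit its SAE rows?** No. If it did, the any-AE and any-TEAE rows would be the same row.

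**3. Can a dosed patient carry a pre-dose SAE?** Yes. Screening takes place "within 28 days prior to first dose" (Protocol 6.1). Under Protocol 7.4, a patient whose first infusion is delayed by an acute or comorbid condition "may remain eligible up to an additional 14 days after the end of the Screening Period without having to rescreen". Anyone then dosed enters the Safety Population (SAP 3.2.3). Screen failures do not.

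**4. Would a treatment-emergent limit remove such an event?** Yes, unless it worsened. The SAP 2.3.2.2 definition begins "Occur after the first administration of study drug; or" and then adds pre-dose events that worsen in severity, grade or relationship after dosing.

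**5. Size of one event.** One patient as a share of the planned column is 100/n:

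| Column | n | One patient (percentage points) |
|---|---|---|
| Cohort 3, one dose arm | 10 | 10.0 |
| Cohort 2 | 15 | 6.7 |
| Cohort 1 | 20 | 5.0 |
| High dose, all cohorts (20 + 15 + 10) | 45 | 2.2 |
| All patients | 55 | 1.8 |

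**6. Share of the collection window that is pre-dose.** The formula is pre-dose days / (pre-dose days + days on study).

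- To Day 364: 28/(28 + 364) = 7.1%; with the 14-day allowance, 42/(42 + 364) = 10.3%.
- To Day 448: 28/476 = 5.9%; 42/490 = 8.6%.

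These shares equal a share of SAEs only if the event rate is constant and every patient uses the whole window. They are close to a ceiling.

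**7. Chance that the issue arises at all.** The documents give no pre-dose SAE probability p, so p is an assumption here. The chance of at least one such patient among n is 1 − (1 − p)^n:

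| Assumed p per patient | n = 55 | n = 10 (one Cohort 3 arm) |
|---|---|---|
| 0.5% | 24% | 5% |
| 1% | 42% | 10% |
| 2% | 67% | 18% |
| 5% | 94% | 40% |

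The range is too wide to say whether the tables will be affected.

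**The case against.** The strongest reply is that the tables follow the stated endpoint. The protocol synopsis and SAP 2.3.2 name TEAEs and SAEs side by side, and Protocol 11.2.1 plans incidence rates for both AEs and TEAEs. An all-SAE count is therefore legitimate, and replacing it everywhere would narrow a named endpoint. This stands, and it is why the fix adds a count and keeps the existing one.

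The listing also marks onset, so with about 55 patients a reader can separate the events by hand. No information is lost. This stands too, but it leaves the by-dose percentage itself mixed.

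Three stronger readings are tempting and are not supported:

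- **That the plan attributes pre-dose SAEs to SRK-015.** It does not. The row is labelled as any SAEs, and the Grade 3 and above and drug-related tables are limited to TEAEs.
- **That 7% to 10% of tabulated SAEs will be pre-dose.** Exclusion criterion 3 bars acute conditions and the need for inpatient observation within 14 days of Screening. Protocol 7.4 permits dosing only after the event resolves and if judged safe. The 28 days is a maximum, and the 42 days applies only to delayed patients.
- **That all the SAE rows are equally exposed.** A pre-dose SAE that later led to death or discontinuation in a dosed patient would usually have worsened after dosing, which makes it treatment-emergent. Those two rows already have TEAE counterparts.

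Finally, SAP Section 7 places the table shells in stand-alone documents not available here. They may already use TE-SAE, but SAP 3.6.1 does not require it.

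**Conclusion.** The point holds as a specific and inexpensive improvement. SAP 3.6.1 tabulates SAEs by preferred term, and in the any-SAE overview row, by cohort and dose with no treatment-emergent limit, while only the listing separates pre-treatment onset. The plan therefore does not require any SAE incidence by dose that is free of pre-dose events.

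The effect requires a dosed patient whose only SAE began before the first dose and did not worsen afterwards. The sizes in step 5 assume the planned enrolment. With no such patient, nothing changes. The point does not touch the efficacy analyses, the sample size or the safety review process.

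**What to change.** In SAP 3.6.1:

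1. Add an overview row for any treatment-emergent SAEs (TE-SAEs).
2. Make the SAE table by system organ class and preferred term a TE-SAE table.
3. Keep the all-SAE count as a clearly labelled row. Leave the death and discontinuation rows as they are, so that the AE and SAE versions stay consistent with each other.
4. Show SAEs with onset before the first dose in a separate count and in the listing.

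Cite SAP 2.3.2.2 as the definition, and first reconcile it with Protocol 10.2.1.5. The protocol counts a pre-dose event as treatment-emergent if its severity increases during the Safety Follow-up Period. The SAP counts worsening in severity, grade or relationship at any time after dosing.

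The cost is one extra row or table and SAE figures by dose that may be slightly lower. The onset flag is already needed for the listing, so no new data are required. Ambiguous events are not lost: under SAP 3.1.7.1 an event with a missing start date counts as treatment-emergent unless the partial date rules that out. For analyses already past database lock, the added tables can be recorded in the study report, as SAP Section 1 provides.
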